Appendix 2 **Telephone Interviews**

The purpose of this interview is to identify any new or worsening neurological symptoms that warrant an unscheduled visit and to collect data on possible events of infections.

Telephone interviews should be performed by study personnel every 4 weeks between clinic visits.

Please ask the following questions and record patient's answers during the Telephone Interview:

Questions: No / Yes

1. Since your last visit or telephone interview, have you had any new or worsening medical problems (such as sudden changes in your thinking, alterations in your behavior, visual disturbances, extremity weakness, limb coordination problems, or gait abnormalities) that have persisted over more than one day?
2. Since your last visit or telephone interview, have you had any signs of infection?
3. Since your last visit or telephone interview, have you had any other new or worsening medical problems or conditions (including pregnancy), surgery, or hospitalization?
4. Since your last visit or telephone interview, have you taken any new medicines (including medicines to treat cancer or MS or any other new medicines that weaken your immune system or steroid medicines other than for the treatment of a recent relapse)?

If the patient answered YES to any question, contact the Investigator and review the patient's answers. The Investigator can determine if an unscheduled visit is required. Please record any relevant safety information in the appropriate eCRF form.

Record any pertinent comments made by the patient during the interview:

Patient ID:

NAME: _____ Date: _____

Name of person completing the telephone interview

5/Statistical Analysis Plan BN29739

Clinical Study Report: ocrelizumab - F. Hoffmann-La Roche Ltd
Protocol BN29739 Report Number 1079337

1. **BACKGROUND**

This Phase IIIb, multicenter, randomized, open-label study is designed to evaluate immune response to vaccines in patients with relapsing forms of multiple sclerosis (MS) after administration of a dose of ocrelizumab.

The clinical cutoff date (CCOD) will be the earliest date on which all randomized patients will have completed the Week 24 visit for Group A, completed the Week 12 visit for Group B, or prematurely discontinued during the Immunization Study Period (ISP) if they have discontinued before the Week 24 visit for Group A or before the Week 12 visit for Group B.

The scope of this statistical analysis plan includes the following:

- The primary analysis of immunology and safety endpoints evaluated in the ISP
- Analysis of all data available at the CCOD from the following periods:
 - The Optional Ocrelizumab Extension (OOE) after completing the ISP
 - The Safety Follow-Up (SFU) Period after the ISP for patients who did not enter the OOE
 - The SFU Period after completing the OOE

2. **STUDY DESIGN**

This Phase IIIb, multicenter, randomized, open-label study is designed to evaluate immune response to vaccines after administration of a dose of ocrelizumab.

The study consists of the following periods: Screening, an ISP, an OOE, SFU, and a Continued B-cell Monitoring Period.

Following screening, approximately 100 adult patients will be randomized into Groups A and B (2:1 active:control) to compare responses to immunization. Patients in Group B are to receive immunization with tetanus toxoid (TT)-containing adsorbed vaccine, 23-valent pneumococcal polysaccharide vaccine (23-PPV), influenza vaccine, and repeated administration with keyhole limpet hemocyanin (KLH). Group B patients will not receive ocrelizumab, but will remain treatment-naïve or continue with interferon beta (IFN- β) treatment until optional ocrelizumab treatment at the end of the ISP.

Patients in Group A are to first receive a 600 mg dose of ocrelizumab, 300mg on Day 1 (Infusion 1) and 300mg on Day 15 (Infusion 2), and starting 12 weeks after Day 1 (Infusion 1 of ocrelizumab) are to receive a similar immunization course to Group B. Group A will be further subdivided into two groups (non-randomly, based on seasonality considerations) to evaluate the effectiveness of a booster 13-valent pneumococcal conjugate vaccination (13-PCV; Group A1) or influenza vaccination (Group A2). For additional details, see the protocol and Schedule of Assessments.

2.1 PROTOCOL SYNOPSIS

The Protocol Synopsis is in [Appendix 1](#). Please note that, in the event that the version of the protocol synopsis in [Appendix 1](#) differs from the version in the current protocol, then the version in the current protocol takes precedence over the version included in this Statistical Analysis Plan (SAP). [Appendix 1](#) will only be updated in the event that the protocol synopsis amended in the future and includes changes that impact this SAP.

2.2 OUTCOME MEASURES

2.2.1 Primary Immunization Outcome Measure

The primary outcome measure is the proportion of patients in Groups A (i.e., combined Groups A1 and A2) and B with a positive response (IgG) to TT vaccine measured 8 weeks after TT vaccine administration (defined fully in Section [4.4.1](#)).

2.2.2 Secondary Outcome Measures

The secondary outcome measures are as follows:

- TT response

The proportion of patients in Groups A (A1 and A2 combined) and B with a positive response (IgG) to TT vaccine measured 4 weeks after booster TT vaccine administration (defined fully in Section [4.4.2.1](#))

Mean levels of anti-tetanus antibody in patients in Groups A (A1 and A2 combined) and B measured immediately prior to and 4 weeks after a booster TT vaccine

- 23-valent pneumococcal polysaccharide vaccine (23-PPV) response and 13-PCV booster response:

The proportion of patients in Groups A1, A2, A (A1 and A2 combined), and B with positive responses against an individual anti-pneumococcal antibody serotype measured 4 weeks after the 23-PPV (23 serotypes) (defined fully in Section [4.4.2.2](#))

The proportion of patients in Groups A1, A2, A (A1 and A2 combined), and B with a positive response against at least 2 out of the 23 serotypes measured 4 weeks after and 8 weeks after administration of the 23-PPV vaccine (defined fully in Section [4.4.2.2](#))

The proportion of patients in Groups A1, A2, A (A1 and A2 combined), and B with positive responses against at least 50% of the serotypes (≥ 12 of 23) measured 4 weeks after administration of the 23-PPV vaccine (defined fully in Section [4.4.2.2](#))

The proportion of patients in Groups A1, A2, A (A1 and A2 combined), and B with positive responses against each of the 23 serotypes measured 8 weeks after patients received the 23-PPV vaccine (which is 4 weeks after Group A1 received the booster 13-PCV) (defined fully in Section [4.4.2.2](#))

Mean levels of anti-pneumococcal antibody (23 serotypes) in patients in Groups A1, A2, A (A1 and A2 combined), and B measured immediately prior to, 4 weeks after and 8 weeks after patients received the 23-PPV (this is 4 weeks after Group A1 received the 13-PCV immunization)

- KLH

Mean levels of anti-KLH antibody (IgG) in patients in Groups A (A1 and A2 combined) and B measured immediately prior to the first administration of KLH and 4 weeks after the last administration of KLH

Mean levels of anti-KLH antibodies (IgG and IgM) in Groups A (A1 and A2 combined) over time at 4, 8, and 12 weeks after first KLH immunization

- Influenza vaccine response:

Proportion of patients in Groups A2 and B who achieve seroprotection defined as specific hemagglutination inhibition (HI) titers >40 at 4 weeks post-immunization

Proportion of patients in Groups A2 and B who achieve a 2-fold increase in specific HI titers at 4 weeks post-immunization

Proportion of patients in Groups A2 and B who achieve a 4-fold increase in specific HI titers at 4 weeks post-immunization

Proportion of patients in Groups A2 and B with seroconversion (i.e., a pre-vaccination antibody titer <10 and a post-vaccination HI titer >40)

Strain-specific geometric mean titers (GMTs) in patients in Groups A2 and B at baseline and Week 4

Strain-specific GMT ratio (post-vaccination:pre-vaccination) in patients in Groups A2 and B

- Magnetic resonance imaging (MRI) assessments in patients in Groups A (A1 and A2 combined) and B to evaluate the long-term effects of ocrelizumab on MRI parameters of disease activity and progression during the OOE

2.2.3 Immunophenotyping Outcome Measures

The humoral and cellular immunity outcome measures in this study are as follows:

- Flow cytometry panel (i.e., circulating B cells and T cells), which will include (but is not limited to) the following cells:

Total B cells (CD19+)

B-cell subsets (e.g., memory B cells, naïve B cells, and plasma cells)

Total T cells (CD3+)

T helper cells (CD3+ and CD4+)

Cytotoxic lymphocyte T (CD3+and CD8+)

Natural killer cells (CD3– and CD16/56+)

- Quantitative Ig: Ig levels (including total Ig, IgG, IgG subtypes, IgM, and IgA)

Ocrelizumab—F. Hoffmann-La Roche Ltd

8/Statistical Analysis Plan BN29739

Clinical Study Report: ocrelizumab - F. Hoffmann-La Roche Ltd

Protocol BN29739 Report Number 1079337

2128

2.2.4 Safety Outcome Measures

The safety outcome measures for this study are as follows:

- Vital signs pre-, during, and post-infusion
- Hematologic laboratory tests
- Anti-drug antibody (ADA) formation
- Urinalyses
- Incidence and severity of adverse events associated with ocrelizumab and study immunizations

2.3 DETERMINATION OF SAMPLE SIZE

For the positive response to TT-containing adsorbed vaccine measured 8 weeks after the administration of vaccine, if both the control and active (ocrelizumab) groups have 70% response rates, the expected half-width of the resulting 95% CI of the difference of 2 response rates is 0.201. To achieve this precision, approximately 100 patients will be enrolled using a 2:1 randomization ratio into active ocrelizumab (Group A) and control (Group B) groups.

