3. STUDY DESIGN

3.1 DESCRIPTION OF STUDY

This Phase IIIb, multicenter, randomized, open-label study is designed to evaluate immune response to vaccines after administration of a dose of OCR (i.e., a dual infusion of OCR 300 mg on Day 1/Week 1 [Dose 1 Infusion 1] and Day 15/Week 2 [Dose 1 Infusion 2]) in patients with RMS.

Following screening, approximately 100 adult patients will be randomized into Groups A and B (2:1; active:control) to compare responses to immunization. Patients in Group B are to receive immunization with TT-containing adsorbed vaccine, 23-PPV, influenza vaccine, and repeated administration with KLH. Group B patients will not receive OCR but will remain on no MS-specific disease-modifying therapy (DMT) or continue with IFN- β treatment until optional OCR treatment at the end of the Immunization Study Period.

Patients in Group A are to first receive OCR (Day 1/Week 1 [Dose 1 Infusion 1] and Day 15/Week 2 [Dose 1 Infusion 2]), and 12 weeks post-OCR treatment, are to receive a similar immunization course to Group B. Group A will be further subdivided into two groups to evaluate the effectiveness of a booster 13-PCV vaccination or of influenza vaccination.

For the primary objective and for secondary objectives 1 and 3 (see Sections [2.1](#) and [2.2](#), respectively), Group A (active) will be compared with Group B (control).

To determine the outcomes of secondary objectives 2 and 4, patients in Group A will be split into two groups with 50% of patients in each group (Groups A1 and A2). Patients will be assigned to either Group A1 or A2:

- Group A1 will receive booster 13-PCV (approximately 33 patients)
- Group A2 will receive the influenza vaccine (approximately 33 patients but a minimum of 30 patients).

A minimum of 30 patients will be assigned to Group A2 during the first influenza season. If a minimum of 30 patients (a maximum of 33) are assigned to Group A2 and receive the first year's influenza vaccine, all remaining patients in Group A will be assigned to

Group A1 and receive the 13-PCV booster. If less than 30 patients have been assigned to Group A2 during the first influenza season, further patients assigned to Group A2 will have influenza vaccine visits during the subsequent influenza season (i.e., when the next year's vaccine becomes available).

The primary and secondary humoral immunity and immunophenotyping outcomes are to be measured by flow cytometry and quantitative Ig measurements.

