6. STATISTICAL CONSIDERATIONS AND ANALYSIS PLAN

6.1 DETERMINATION OF SAMPLE SIZE

Approximately 100 patients will be enrolled using a 2:1 randomization ratio into active (Group A) and control (Group B) groups. For the positive response to TT-containing adsorbed vaccine measured 8 weeks after the administration of vaccine, if both the control and active (OCR) groups have 70% response rates, the expected half width of the resulting 95% CI of the difference of two response rates is 0.201.

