4.1.2 Observed Cases Population

The Observed Cases (OC) Population is defined as all randomized patients who complete the ISP. Patients who receive an incorrect medication or vaccination rather than the one that they are assigned to will be summarized according to their randomized treatment group.

All immunization outcome measures will be analyzed using the OC Population.

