4.4.1 Primary Immunology Endpoint

The primary outcome measure is the proportion of patients in Groups A and B with a positive response (IgG) to TT adsorbed vaccine measured 8 weeks after TT booster vaccine administration. Positive response is defined as follows:

- For patients with pre-immunization tetanus antibody titers <0.1 IU/mL, a positive response to the booster TT immunization is defined as an antibody titer ≥ 0.2 IU/mL measured 8 weeks after immunization.
- For patients with pre-immunization tetanus antibody titers ≥ 0.1 IU/mL, a positive response to the booster TT immunization is defined as a 4-fold increase in antibody titers measured 8 weeks after immunization compared with pre-immunization levels.

The number and proportion of patients with a positive response to TT adsorbed vaccine will be presented by treatment group. The difference between treatment groups A and B in positive response rates and the associated 95% CI will also be presented using a normal approximation method.

Levels of anti-tetanus antibody in patients in Groups A and B measured 8 weeks after a booster TT vaccine administration will be summarized descriptively by treatment, showing the following summary statistics:

- Number and percentage of patients with values \leq LLQ
- Number and percentage of patients with values $>$ LLQ
- Geometric mean of known values $>$ LLQ
- 95% CI for geometric mean of known values $>$ LLQ, calculated using a normal approximation method on the log scale and then back-transformed to the original scale
- Geometric mean of all nonmissing values, imputing $LLQ \div 2$ for values \leq LLQ
- 95% CI for geometric mean of all nonmissing values, imputing $LLQ \div 2$ for values \leq LLQ, calculated using a normal approximation method on the log scale and then back-transformed to the original scale
- Median of known values $>$ LLQ
- Median of all nonmissing values, imputing $LLQ \div 2$ for values \leq LLQ

To aid comparison back to pre-vaccination levels, the following pre-vaccination summary statistics will also be included in the tabular summary at 8 weeks:

- Geometric mean of known pre-vaccination values $>$ LLQ
- Geometric mean of all nonmissing pre-vaccination values, imputing $LLQ \div 2$ for values \leq LLQ

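### The stated 95% CI half-width of 0.201 cannot be reproduced from about 100 patients at 2:1 (0.191); it is the value for 60 v 30 = 90 patients, and no allowance for non-evaluable patients is stated

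*SAP*

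**What the plan says.** SAP 2.3 sets the scenario, "if both the control and active (ocrelizumab) groups have 70% response rates", and states that "the expected half-width of the resulting 95% CI of the difference of 2 response rates is 0.201". The next sentence ties this to the size of the trial: "To achieve this precision, approximately 100 patients will be enrolled using a 2:1 randomization ratio". Protocol 6.1 gives the enrolment target first and then the same result: "the expected half width of the resulting 95% CI of the difference of two response rates is 0.201". The sample-size paragraph of the protocol synopsis agrees.

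For the primary endpoint, SAP 4.4.1 specifies the difference in response rates between Groups A and B, and "the associated 95% CI will also be presented using a normal approximation method". SAP 4.4 rules out hypothesis testing.

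The patients who enter that interval are fewer than those randomized if anyone is lost. SAP 4.1.2 says: "The Observed Cases (OC) Population is defined as all randomized patients who complete the ISP". All immunization outcomes are analysed in that population. SAP 4.4 also drops patients whose immunology assessment is missing, and SAP 4.7 rules out imputation. Protocol 4.8.1 does not replace withdrawals. Neither sample-size section gives an evaluable number or an expected rate of loss.

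**The concern.** With no test, power or margin, the expected half-width is the only quantitative justification for the number of patients. Protocol 3.1 also sets target counts for Groups A1 and A2, but attaches no precision or power to them. A reader who puts the stated inputs into the stated interval method does not get the stated result.

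The reader also cannot tell whether 0.201 describes the patients enrolled or the patients analysed. This decides how much loss the design was meant to absorb before the target is missed: about 10 patients if the figure was calculated for 90, none if it was meant for 100.

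**Working it through.** **Inputs**
- Response rates 0.70 and 0.70 (SAP 2.3, Protocol 6.1).
- 95% interval, taken as two-sided, z = 1.96.
- About 100 patients at 2:1 (same sections), so 67 v 33. The counts in Protocol 3.1 (about 33 in A1 plus about 33 in A2) suggest 66 v 33.
- Normal-approximation interval (SAP 4.4.1). No continuity correction is mentioned.

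**Formula**

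Half-width = 1.96 × √[0.7 × 0.3 × (1/nA + 1/nB)]

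**The plan's figure at its stated number of patients**
- 67 v 33: 1.96 × √[0.21 × (1/67 + 1/33)] = 1.96 × √0.009498 = 0.1910
- 66 v 33: 1.96 × √[0.21 × (1/66 + 1/33)] = 1.96 × √0.009545 = 0.1915

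Neither is 0.201.

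**The number of patients that gives 0.201**

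At exact 2:1, 1/nA + 1/nB = 4.5/N, so N = 0.21 × 1.96² × 4.5 / h². With h = 0.201, N = 89.9. Half-widths from 0.2005 to 0.2015 need N from 90.3 down to 89.4, so 90 is the only whole total that rounds to 0.201.
- 60 v 30: 1.96 × √[0.21 × (1/60 + 1/30)] = 1.96 × √0.0105 = 0.2008

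**Can *approximately* cover the gap?** No. At 2:1, totals from 95 to 105 give 0.1955 down to 0.1859.

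**Can another interval method cover it?** Half-widths at 67 v 33 and 70% response, unless noted:

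| Method | Half-width |
|---|---|
| Normal approximation (SAP) | 0.1910 |
| With continuity correction | 0.2136 |
| Hauck-Anderson | 0.209 |
| Exact unconditional score | about 0.195 |
| t quantile | 0.1934 |
| Variance with n − 1 | 0.1935 |
| Agresti-Caffo | 0.1880 |
| Newcombe (mean of the two arms) | 0.1851 |
| Mee score | 0.1885 |
| Miettinen-Nurminen | 0.1894 |
| Normal approximation, averaged over the binomial | 0.1883 |
| 50 v 50, normal approximation | 0.1796 |
| 50 v 50, continuity correction | 0.1996 |

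None gives 0.201 at about 100 patients.

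**Size of the gap**

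0.201 − 0.191 = 0.010, and 0.201/0.191 = 1.05, so the stated half-width is about 5% wider than 100 evaluable patients would give. In patients, 90/100 = 0.90, which is what a 10% loss would leave.

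**The case against.** The strongest reply is that 100 is an enrolment target in all three places. No sentence says that 100 evaluable patients enter the calculation. The analysis is confined to completers with data and withdrawals are not replaced, so fewer than 100 analysed patients are to be expected. Since 60 v 30 is 90% of 100 at the same ratio, the simplest explanation is that 0.201 was calculated for 90 evaluable patients and enrolment was raised to 100 to cover loss. On that reading the figure is right and an assumption was left out. This is plausible, but it remains an inference: neither document gives a loss rate or an evaluable number.

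The reply is also right about the consequences. The gap is on the safe side, and no margin or success threshold depends on 0.201. The assumed response rate matters more: at 50% in both groups, 67 v 33 gives 0.208. The trial is also well advanced. SAP 3.1 describes randomization in the past tense, and Protocol 1.1.4 and 5.1.1.6 already report results from the Immunization Study Period. The achieved interval, which SAP 4.4.1 requires, will replace the planned one.

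Three stronger readings are tempting and not supported.
- A reader might infer that the trial is too small for its stated precision. The opposite holds: with 100 evaluable patients it does better than stated.
- A reader might infer that the SAP claims 100 patients are necessary for 0.201. It says that about 100 will be enrolled to achieve it, not that fewer would fail.
- A reader might infer that enrolment is 10 patients too large. That holds only if nobody is lost, which the choice of analysis population does not assume.

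What stands is narrower: the figure and the number of patients are printed together, and the step that connects them is missing.

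**Conclusion.** The point holds as a reproducibility defect in the plan's only precision figure. At about 100 patients and 2:1, the SAP's own interval has a half-width of 0.191, while 0.201 belongs to 60 v 30 = 90 patients. The difference is 0.010 in half-width, or 10 patients, and it is conservative.

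The result rests on 70% response in both groups, a two-sided 95% level, and the uncorrected normal approximation. That 90 stands for 10% non-evaluable is the likely explanation, but the documents do not establish it. Nothing here puts enrolment, the analysis method or the interpretation of results in doubt.

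**What to change.** Change one sentence in the synopsis, in Protocol 6.1 and in SAP 2.3, with the same wording in each. There are two options, and the sponsor's own sizing calculation decides between them:
- State a half-width of 0.191 for 67/33 evaluable patients.
- Keep 0.201 and state that it is for about 90 evaluable patients (60/30) in the Observed Cases Population, which assumes that about 10% of the 100 enrolled are non-evaluable.

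Either version should name the interval method and say that the numbers are of analysed patients. The cost is editorial: no change to enrolment, conduct or analysis.

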2.4 ANALYSIS TIMING

The primary analysis of immunology and safety endpoints evaluated in the ISP and the analysis of available OOE data will be performed at the CCOD, which is defined as the date when all randomized patients have completed the Week 24 visit for Group A or the Week 12 visit for Group B, or the date on when all randomized patients have prematurely discontinued the ISP if they have discontinued before the Week 24 visit for Group A or before the Week 12 visit for Group B.

Regular interim safety analyses may be performed, approximately every 6 months, to allow pooled safety analyses of MS patients treated with ocrelizumab. These analyses are not described in this document.

Interim pharmacokinetic (PK) analyses may also be performed during the study. These PK analyses are not described here but in a separate document.

3. STUDY CONDUCT

3.1 RANDOMIZATION ISSUES

Patients were randomized into two groups (Group A or Group B) in a 2:1 randomization ratio. Randomization was performed by an independent vendor via an interactive response system.

4. STATISTICAL METHODS

Except where stated otherwise, all tabular and graphical summaries of data, which are presented by treatment group, will separately show results from the following four groups:

- Group A1 (ocrelizumab + 13-PCV vaccine)
- Group A2 (ocrelizumab + influenza vaccine)
- Group A overall (Groups A1 + A2)
- Group B (control)

All listings will show study data for each treatment group in the order shown above.

